### Important Instructions for Using This Protocol Template:

1. Add this completed protocol template to your study in CATS IRB (<http://irb.psu.edu>) on the “Basic Information” page, item 7.
2. This template is provided to help investigators prepare a protocol that includes the necessary information needed by the IRB to determine whether a study meets all applicable criteria for approval.
3. **Type your protocol responses below the gray instructional boxes of guidance language. If the section or item is not applicable, indicate not applicable.**
4. **For research being conducted at Penn State Hershey or by Penn State Hershey researchers only, delete the instructional boxes from the final version of the protocol prior to upload to CATS IRB (<http://irb.psu.edu>). For all other research, do not delete the instructional boxes from the final version of the protocol.**
5. When making revisions to this protocol as requested by the IRB, please follow the instructions outlined in the Study Submission Guide available in the Help Center in CATS IRB (<http://irb.psu.edu>) for using track changes.

### If you need help...

## 1.0 Objectives

### 1.1 Study Objectives

Assess the efficacy of the vein visualization device AccuVein (AccuVein, Inc., Huntington, NY) in comparison to a standard technique for establishing intravenous (IV) access in the infant population (<2 years old)

### 1.2 Primary Study Endpoints

Success Rate of IV Insertion within three allowed attempts

### 1.3 Secondary Study Endpoints

Total number of attempts and time to successful insertion

## 2.0 Background

### 2.1 Scientific Background and Gaps

Children undergoing aesthesia procedures need intravenous access. This may be done after anesthesia induction in infants. This may be challenging in the infant population under anesthesia when establishing IV access rapidly is paramount, as emergency drugs may need to be administered if a complication were to occur at induction. The infant population is especially challenging in this regard due to increased body fat.

### 2.2 Previous Data

The success rate at first attempt IV induction in children varies from 32 – 92% depending on provider experience. Various techniques have been tried in the past that include application of warming devices and use of ultrasound. Recent literature suggests use of infrared illumination to aid vein visualization, with a device such as the AccuVein (AccuVein, Inc., Huntington, NY), has been successfully used.

### 2.3 Study Rationale

There are few reports of use of the AccuVein device in the infant population. Our experience with this device in infant population has been positive. Additionally, we think that this will be a good learning tool for residents to help identify a target vein for IV access.

## 3.0 Inclusion and Exclusion Criteria

### 3.1 Inclusion Criteria

1. Age: birth to <2years of age
2. Sex: male or female
3. Undergoing anesthesia procedures at Penn State Health, Hershey Medical Center and Penn State Children's Hospital
4. ASA physical status 1,2 or 3
5. Parent/guardian fluent in written and spoken English

### 3.2 Exclusion Criteria

1. Age: ≥2 years of age
2. Emergency procedures requiring anesthesia

2. ASA physical status 4
3. Patients with pre-existing IV access (IV access in situ)

### **3.3 Early Withdrawal of Subjects**

#### **3.3.1 Criteria for removal from study**

1. Withdrawal of parental permission
2. Child develops significant laryngospasm that needs intervention with succinylcholine

#### **3.3.2 Follow-up for withdrawn subjects**

Not applicable

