## 7.2 Study Procedures

### 7.2.1 Day of Surgery

After obtaining informed consent, the infant will be randomized to the vein visualization or standard group based on a computer generated number.

Standard anesthesia induction procedures will be used. This includes application of standard ASA monitoring at induction and standard inhalation induction with sevoflurane.

Once the subject is deemed ready for intravenous access attempt, a tourniquet will be applied on the corresponding limb where IV access is contemplated.

For those randomized to the control group (standard technique group), the standard technique for establishing IV access will be used. The standard technique involves directly identifying the vein after application of a tourniquet, cleaning with alcohol and then siting the intravenous catheter.

For those randomized to the vein visualization group, the AccuVein device will be used as an aid to identify the vein after application of a tourniquet. The technique of actual insertion of the intravenous catheter will be the same as the standard technique. The device will be used to better visualize and identify the vein.

If, after 3 needle sticks, IV access has not been established using the technique for the group to which the subject was assigned (standard or vein finder), the care provider will use the other technique (standard or vein finder) to attempt to insert the IV line.

In order to avoid operator variation, the intravenous catheter will be inserted by an experienced pediatric anesthesiologist who is a member of the research team. Currently all the pediatric anesthesia faculty members are familiar with, and have used, the vein finder in case of difficult intravenous access. If a complication develops while attempting to start an IV using the vein finder or standard technique, and a rapid IV access is needed, it will be at the attending anesthesiologist's discretion to perform the IV rapidly with either technique, since our faculty anesthesiologists are proficient with both techniques. Multiple anesthesiologists may attempt the IV simultaneously. This is how we would normally manage this situation and is the standard of care. If this happens we will withdraw the child from the study.

Data to be collected:

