## 8.0 Subject Numbers and Statistical Plan

### 8.1 Number of Subjects

A sample size of 160 patients to include a 15% margin above the number indicated by the sample size determination, to allow for subject withdrawal or situations of incomplete subject data.

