## 10.0 Data and Safety Monitoring Plan

## 11.0 Risks

Loss of confidentiality is a potential risk when conducting human subject search.

Increase in the number of IV access attempts and/or time to successful IV placement.

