## 19.0 Adverse Event Reporting

### 19.1 Reporting Adverse Reactions and Unanticipated Problems to the Responsible IRB

In accordance with applicable policies of The Pennsylvania State University Institutional Review Board (IRB), the investigator will report, to the IRB, any observed or reported harm (adverse event) experienced by a subject or other individual, which in the opinion of the investigator is determined to be (1) unexpected; and (2) probably related to the research procedures. Harms (adverse events) will be submitted to the IRB in accordance with the IRB policies and procedures.

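### Children withdrawn after randomization for a clinical event: nothing requires their IV outcome, sticks, time or reason for withdrawal to be recorded or analysed

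*Combined protocol and SAP*

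**What the plan says.** Section 7.2.1 places randomization after parental permission and before the inhalation induction. Three routes out of the study follow.

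- Section 3.3.1 lists two: "Withdrawal of parental permission" and "Child develops significant laryngospasm that needs intervention with succinylcholine".
- Section 7.2.1 adds a third that is not on that list: "If a complication develops while attempting to start an IV using the vein finder or standard technique, and a rapid IV access is needed". In that case the attending may use either technique, several anesthesiologists may attempt at once, and "If this happens we will withdraw the child from the study".

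Section 3.3.2, "Follow-up for withdrawn subjects", is answered as not applicable. Section 8.1 adds a 15% margin to the sample size "to allow for subject withdrawal or situations of incomplete subject data". Section 8.3 names a chi-square test and ANOVA, but no analysis set and no rule for missing outcomes.

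The data-collection text at the end of 7.2.1 covers time from first skin contact, success by saline flush, and site. It neither includes nor exempts withdrawn children. It does keep children with three failed sticks in the study: they cross to the other technique and their time is noted. Section 11.0 gives the procedural risk as "Increase in the number of IV access attempts and/or time to successful IV placement".

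**The concern.** Two of the three exits are clinical events that can occur after assignment and close to IV placement. The one in 7.2.1 by definition occurs while the assigned technique is in use. If searching takes longer or more sticks are needed in one arm, there is more time without access in which a complication can become urgent. Removal from the study can then depend on both the arm and the outcome, and comparing only the remaining children no longer has the protection of randomization.

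The primary endpoint (success within three attempts, section 1.2) and both secondary endpoints (attempts and time, section 1.3) are exposed. Attempts and time are also what section 11.0 names as the study's risk. Staff who read 3.3.2 as it stands could reasonably stop recording when a child is withdrawn, and attempts and times missed in the operating room may not be recoverable later.

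**Working it through.** **Plan's own figures.** Section 8.2 gives 90% success, 95% confidence and 139 children. It gives no control rate, power or precision.

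- A one-proportion precision formula with an assumed half-width d of 0.05 gives 1.96² × 0.90 × 0.10 / 0.05² = 138.3, rounded up to 139. The half-width is my assumption: d = 0.04 gives 217 and d = 0.06 gives 97.
- Section 8.1: 139 × 1.15 = 159.85, rounded up to 160.
- Margin: 160 - 139 = 21, and 21/160 = 13.1% of those enrolled.

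So the stated target is met even if 21 enrolled children contribute no outcome.

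**What each exit implies.**

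| Exit | Where stated | Can it depend on technique? | Is recording required? |
|---|---|---|---|
| Parental permission withdrawn | 3.3.1 | Not evidently | Not stated; data use may end |
| Laryngospasm needing succinylcholine | 3.3.1 | Less likely if before any skin contact; possible if during a long search | Not stated |
| Complication during the attempt, rapid access needed | 7.2.1 only | Yes, it arises during the attempt | Not stated |
| Three failed sticks | 7.2.1 | Yes | Stays in; time noted |

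Only the second and third rows are at issue.

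**How far missing outcomes could move the primary comparison.** Assumptions, none of them in the documents: 80 per arm (the allocation ratio is not stated) and 90% success among retained children in both arms (section 8.2 gives 90% for the device only). The retained-only difference is then 0. Let a and b be the numbers withdrawn without an outcome in arms A and B. The as-randomized difference, A minus B, lies between

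- lower: 0.9(80 - a)/80 - [0.9(80 - b) + b]/80
- upper: [0.9(80 - a) + a]/80 - 0.9(80 - b)/80

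| a, b | Lower | Upper |
|---|---|---|
| 4, 4 | 0.855 - 0.905 = -5.0 points | 0.905 - 0.855 = +5.0 points |
| 0, 8 | 0.900 - 0.910 = -1.0 point | 0.900 - 0.810 = +9.0 points |
| 10, 11 (whole margin) | 0.7875 - 0.91375 = -12.6 points | 0.9125 - 0.77625 = +13.6 points |

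These are worst-case bounds, not estimates of bias. The 0, 8 row shows that imbalance matters as well as number: eight losses in one arm shift the range almost wholly to one side.

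**The case against.** The strongest reply is that section 3.3.2 answers a template heading about follow-up. No child here has follow-up, since participation ends with surgery (7.3). The same document marks its recruitment-process and screening sections (4.2, 4.4) as not applicable while describing parts of both elsewhere. On that reading the entry means only that there are no later visits. This stands in part: a reader might infer that data already observed are discarded, or that recording is forbidden, and no section says so. What remains is that nothing requires recording or analysis, while 7.2.1 does remove the child from the study and 8.1 adds children to cover the loss.

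Four further inferences are tempting and not supported.

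- *The hardest cannulations are lost.* They are not: children with three failed sticks stay in and are timed. Laryngospasm is an airway event that may precede any attempt, when there is no stick or time to record.
- *An as-randomized analysis is impossible, or withdrawals cannot be compared by arm.* Assignment is fixed before induction, so withdrawals can be counted by arm from assignment and status alone. A pre-set rule could also code the binary primary endpoint. The plan has no such rule, and coding would not recover attempts or time.
- *Harms in these children go wholly unreported.* Section 19.1 covers any subject, although it sends the IRB only harms judged both unexpected and probably related. Complications are not a listed data item for any child, so that gap is not specific to withdrawal.
- *The margin of 21 exceeds the expected failures (0.10 × 160 = 16), so the loss could swamp the endpoint.* The 21 also covers parental withdrawal and incomplete data, and the 16 assumes 90% in both arms. The comparison measures no bias.

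It is also fair that, after the urgent trigger, sticks and time partly reflect urgent management and not the assigned technique. That limits their value for the technique comparison. It does not justify leaving these children out.

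**Conclusion.** The concern holds in a limited form. The protocol permits loss after randomization that may depend on arm and outcome, and it does not require the IV outcome, sticks, time or reason to be kept or analysed for children withdrawn for laryngospasm or urgent access. An unbiased as-randomized comparison of success, attempts and time is therefore not assured; the documents do not show that it is biased.

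The number of such withdrawals is not stated and may be small. The 13.1% margin is a ceiling that the plan allows for all causes together. Under the assumptions shown, the possible effect on the success difference runs from about 5 points either way (four per arm) to about 13 points either way (the whole margin). Separately, the withdrawal list in 3.3.1 and the trigger in 7.2.1 do not match. The change should be made: it is inexpensive and needs to be in place before data are collected.

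**What to change.** In section 3.3.2, replace the present entry with wording to this effect: unless parental permission for data use is withdrawn, record until IV access is established the number of sticks by technique, the technique in use at the event, the technique that succeeded, the time from first skin contact (if any attempt was made), and the complication or reason for withdrawal. Keep these children in their randomized arm for analysis, and report withdrawals and their reasons by arm.

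For the clinical triggers, describe the child as having discontinued the assigned technique, not as withdrawn from the study. Reconcile the list in 3.3.1 with the trigger in 7.2.1. Clinical management is unchanged.

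The cost is protocol wording, a few fields on the data form and a line in the parental permission form. The team already present observes these events, so no extra procedure or staff is needed. The limitation is that data after an urgent event partly reflect urgent management; recording the technique in use at the event and the one that succeeded lets the analysis show this.

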## **4.0 Recruitment Methods**

### **4.1 Identification of subjects**

Potential subjects will be identified from the electronic operating room scheduling system (surginet) by reviewing the operative list schedule the day before or on the day of their scheduled surgical or diagnostic procedure.

### **4.2 Recruitment process**

Not applicable

### **4.3 Recruitment materials**

Not applicable

### **4.4 Eligibility/screening of subjects**

Not applicable

## **5.0 Consent Process and Documentation**

### **5.1 Consent Process**

#### **5.1.1 Obtaining Informed Consent**

##### **5.1.1.1 Timing and Location of Consent**

The parental permission for research will be obtained on the day of the procedure during the pre-anesthesia evaluation.

##### **5.1.1.2 Coercion or Undue Influence during Consent**

Parents and legal guardians of patients that are enrolling in the study will be told that participation is voluntary and will not in any way compromise the standard of care that the patient will receive.

#### **5.1.2 Waiver or alteration of the informed consent requirement**

We are requesting a partial waiver of consent for recruitment to screen medical record information to identify subjects meeting the inclusion/exclusion criteria.

## 5.2 Consent Documentation

### 5.2.1 Written Documentation of Consent

Written parental permission for participation in the study will be obtained. An original will be given to the parent/guardian for their records and another original will be kept by the research team. A copy will be uploaded to their medical record.

### 5.2.2 Waiver of Documentation of Consent (Implied consent, Verbal consent, etc.)

N/A

## 5.3 Consent – Other Considerations

### 5.3.1 Non-English Speaking Subjects

N/A

### 5.3.2 Cognitively Impaired Adults

#### 5.3.2.1 Capability of Providing Consent

N/A

#### 5.3.2.2 Adults Unable To Consent

N/A

#### 5.3.2.3 Assent of Adults Unable to Consent

N/A

### 5.3.3 Subjects who are not yet adults (infants, children, teenagers)

#### 5.3.3.1 Parental Permission

Parent or legal guardian will give consent

#### 5.3.3.2 Assent of subjects who are not yet adults

Assent will not be obtained. The capability of these children (taking into account the ages, maturity, and psychological state of the children involved) is so limited that they cannot reasonably be consulted.

## 6.0 HIPAA Research Authorization and/or Waiver or Alteration of Authorization

### 6.1 Authorization and/or Waiver or Alteration of Authorization for the Uses and Disclosures of PHI

Check all that apply:

- Not applicable, no identifiable protected health information (PHI) is accessed, used or disclosed in this study. [Mark all parts of sections 6.2 and 6.3 as not applicable]
- Authorization will be obtained and documented as part of the consent process. [If this is the only box checked, mark sections 6.2 and 6.3 as not applicable]
- Partial waiver is requested for recruitment purposes only (Check this box if patients' medical records will be accessed to determine eligibility before consent/authorization has been obtained). [Complete all parts of sections 6.2 and 6.3]
- Full waiver is requested for entire research study (e.g., medical record review studies). [Complete all parts of sections 6.2 and 6.3]
- Alteration is requested to waive requirement for written documentation of authorization (verbal authorization will be obtained). [Complete all parts of sections 6.2 and 6.3]

## **6.2 Waiver or Alteration of Authorization for the Uses and Disclosures of PHI**

### **6.2.1 Access, use or disclosure of PHI representing no more than a minimal risk to the privacy of the individual**

#### **6.2.1.1 Plan to protect PHI from improper use or disclosure**

Information is included in the “Confidentiality, Privacy and Data Management” section of this protocol.

#### **6.2.1.2 Plan to destroy identifiers or a justification for retaining identifiers**

Identifiers will be destroyed at the completion of the study.

### **6.2.2 Explanation for why the research could not practically be conducted without access to and use of PHI**

Information must be obtained from the subject's electronic medical record during recruitment to determine eligibility and, in some cases, to confirm information discussed with the subject's parent/guardian in regards to their medical history.

### **6.2.3 Explanation for why the research could not practically be conducted without the waiver or alteration of authorization**

The waiver is requested only for recruitment to determine subject eligibility to ensure that no medical conditions that fall into the exclusion criteria are present and would thus preclude enrollment. This waiver will minimize the enrollment of subjects' who may ultimately fail to meet the study inclusion/exclusion criteria.

## **6.3 Waiver or alteration of authorization statements of agreement**

Protected health information obtained as part of this research will not be reused or disclosed to any other person or entity, except as required by law, for authorized oversight of the research study, or for other permitted uses and disclosures according to federal regulations.

The research team will collect only information essential to the study and in accord with the ‘Minimum Necessary’ standard (information reasonably necessary to accomplish the objectives of the research) per federal regulations.

Access to the information will be limited, to the greatest extent possible, within the research team. All disclosures or releases of identifiable information granted under this waiver will be accounted for and documented.

## **7.0 Study Design and Procedures**

### **7.1 Study Design**

This will be a randomized controlled study.

The objective of the study is to assess the efficacy of the vein visualization device in comparison to a standard technique in the infant population (<2years). Subjects will be randomized to the vein visualization or standard group using a computer generated randomization program.

## 7.2 Study Procedures

### 7.2.1 Day of Surgery

After obtaining informed consent, the infant will be randomized to the vein visualization or standard group based on a computer generated number.

Standard anesthesia induction procedures will be used. This includes application of standard ASA monitoring at induction and standard inhalation induction with sevoflurane.

Once the subject is deemed ready for intravenous access attempt, a tourniquet will be applied on the corresponding limb where IV access is contemplated.

For those randomized to the control group (standard technique group), the standard technique for establishing IV access will be used. The standard technique involves directly identifying the vein after application of a tourniquet, cleaning with alcohol and then siting the intravenous catheter.

For those randomized to the vein visualization group, the AccuVein device will be used as an aid to identify the vein after application of a tourniquet. The technique of actual insertion of the intravenous catheter will be the same as the standard technique. The device will be used to better visualize and identify the vein.

If, after 3 needle sticks, IV access has not been established using the technique for the group to which the subject was assigned (standard or vein finder), the care provider will use the other technique (standard or vein finder) to attempt to insert the IV line.

In order to avoid operator variation, the intravenous catheter will be inserted by an experienced pediatric anesthesiologist who is a member of the research team. Currently all the pediatric anesthesia faculty members are familiar with, and have used, the vein finder in case of difficult intravenous access. If a complication develops while attempting to start an IV using the vein finder or standard technique, and a rapid IV access is needed, it will be at the attending anesthesiologist's discretion to perform the IV rapidly with either technique, since our faculty anesthesiologists are proficient with both techniques. Multiple anesthesiologists may attempt the IV simultaneously. This is how we would normally manage this situation and is the standard of care. If this happens we will withdraw the child from the study.

Data to be collected:

The time to successful IV insertion will be from the first time that the canula touches the skin to until successful IV access; up to 3 attempts. After the 3rd attempt, if still unsuccessful, the alternative technique will be used as rescue. Again, time to successful insertion will be noted. Success at IV will be determined by flushability with 5 ml of sterile normal saline. The site(s) of access will also be recorded.

Medical Record Information: This information will include, but is not limited to: Age, gender, physical status, weight, height, skin color, surgical procedure, presenting underlying conditions and co-morbidities.

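### Randomisation is listed before induction with no stated concealment, so infants may be lost before any stick, and readiness, limb and possibly operator can be chosen knowing the arm

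*Combined protocol and SAP*

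**What the plan says.** Permission is sought shortly before anesthesia (section 5.1.1.1): "The parental permission for research will be obtained on the day of the procedure during the pre-anesthesia evaluation".

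Section 7.2.1 then gives the steps in this order:

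1. Allocation: "After obtaining informed consent, the infant will be randomized to the vein visualization or standard group".
2. Inhalation induction, the same in both groups: "Standard anesthesia induction procedures will be used".
3. Readiness and limb: "Once the subject is deemed ready for intravenous access attempt, a tourniquet will be applied on the corresponding limb where IV access is contemplated".
4. Only then the assigned technique. In the device group, AccuVein is used to find the vein once the tourniquet is on.

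Insertion is restricted to experienced pediatric anesthesiologists on the research team, with the declared aim of avoiding operator variation. How and when one is assigned to an infant is not stated.

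Section 3.3.1 removes infants for withdrawn permission, or when this occurs: "Child develops significant laryngospasm that needs intervention with succinylcholine". Neither criterion is tied to a time point. Section 7.2.1 also withdraws a child if a complication during the attempt calls for rapid access. Section 3.3.2 marks follow-up of withdrawn subjects as not applicable. Section 8.1 adds 15% to the sample size "to allow for subject withdrawal or situations of incomplete subject data".

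The protocol describes no allocation concealment, no moment at which the arm is revealed, no criteria for readiness, no rule for choosing the limb and no analysis population.

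**The concern.** The two techniques differ only from the moment the vein is sought. Everything before that is common to both groups, so no one needs to know the arm until then. Allocating earlier opens two gaps.

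The first is loss. An infant removed between allocation and the first stick has no outcome that reflects either technique. Leaving that infant out departs from the randomised set. Counting a failure adds noise unrelated to the technique.

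The second is influence. If the arm is known when readiness is judged, the limb picked or the operator settled, those choices can differ by arm. They plausibly affect the primary endpoint, success within three attempts (section 1.2). Section 2.2 itself reports first-attempt success from 32% to 92% depending on provider experience. Section 7.2.1 records the access site, so an imbalance in site could be seen afterwards, but the chi-square test and ANOVA in section 8.3 would not remove it.

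**Working it through.** **The plan's own numbers.** Section 8.2 gives 90% success on the device, 95% confidence and 139 patients. A single-proportion precision formula reproduces this with an assumed half-width of 0.05, which the plan does not state:

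n = z² p(1 − p)/d² = 1.96² × 0.90 × 0.10 / 0.05² = 138.3, rounded up to 139.

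The margin in section 8.1 gives 139 × 1.15 = 159.85, rounded up to 160. The allowance is 160 − 139 = 21 infants, and 21/160 = 13.1%. It covers withdrawal and incomplete data at any stage. The share falling before the first stick is not given.

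**Upper bound on the cost in power.** Assumptions not in the plan: 1:1 allocation, a two-sided test at 0.05, and control success of 70%, 75% or 80%. With n per arm, difference Δ and mean rate p̄:

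- se0 = √(2 p̄(1 − p̄)/n)
- se1 = √([p1(1 − p1) + p2(1 − p2)]/n)
- power = Φ((Δ − 1.96 se0)/se1)

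For 90% against 75%:

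- 160 analysed (80 per arm): se0 = 0.0601, se1 = 0.0589, (0.15 − 1.96 × 0.0601)/0.0589 = 0.55, power 70.8%.
- 139 analysed (69.5 per arm): se0 = 0.0645, se1 = 0.0632, (0.15 − 1.96 × 0.0645)/0.0632 = 0.37, power 64.6%.

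| Assumed control rate | 139 analysed | 160 analysed | Gain if all 21 losses precede a stick | Gain if half do (149.5 analysed) |
|---|---|---|---|---|
| 70% | 84.6% | 89.3% | 4.7 points | 2.5 points |
| 75% | 64.6% | 70.8% | 6.2 points | 3.2 points |
| 80% | 37.7% | 42.4% | 4.7 points | 2.4 points |

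The gain comes from replacing lost infants, so it requires consenting more of them.

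**Arm-aware choices.** No figure in the documents sizes this. The following only shows how sensitive the result is. Suppose the device has no effect, success is 85% with 80 per arm, and choice of limb or operator raises success in one arm. The chance of a significant result favouring that arm, nominally 2.5%, becomes:

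- 5.5% for a shift of 2 points,
- 15.7% for 5 points,
- 36.5% for 8 points.

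The base rate and the shifts are assumptions, not estimates for this trial.

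**The case against.** The strongest reply is that losses before any stick should not bias the comparison. Both groups have the same induction, and laryngospasm at that stage has no evident route to depend on the arm. A pre-stated analysis set of infants with at least one attempt would then cost only numbers. This stands. A reader might infer that early losses break the randomised comparison, and the documents do not support that.

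Other tempting readings also go too far:

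- **That infants are randomised at consent.** The text says after consent and gives no exact moment. The timing before induction is read from the order of the paragraphs.
- **That some infants will be lost before a stick.** They may be. The criteria in section 3.3.1 have no time point and could also apply during attempts.
- **That the arm is already known when the limb is chosen.** This is inferred from silence on concealment. The protocol does not say who learns the allocation or when.
- **That the operator is picked after allocation.** Nothing says so, and the restriction to experienced team members narrows the room for operator bias.

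It is also fair to say that the more worrying withdrawals are those for complications during the attempt, because they follow exposure to the technique and could depend on the arm. Later allocation leaves them untouched. Only analysing everyone as assigned deals with them.

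Finally, section 2.1 stresses that access must be obtained rapidly, and a reveal after induction adds a step. That cost is real but small if the allocation is prepared beforehand and opened by someone other than the operator.

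What remains is that nothing protects readiness, first limb and possibly operator from knowledge of the arm, although such protection is easy to provide.

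**Conclusion.** The point holds in conditional form and is worth acting on, with medium confidence. As written, allocation comes before induction, readiness and limb choice, with no stated concealment and no analysis set. Infants may be lost in that interval, and arm-aware choices are possible.

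Avoiding early losses is worth at most 4.7 to 6.2 points of power under the assumptions above, and less in practice, because the 21 infants also cover withdrawals during attempts and incomplete data. The case therefore rests mainly on preventing bias whose size the documents cannot give. If the sponsor already conceals the arm until readiness, with operator and limb settled beforehand, a sentence saying so would resolve most of the point. The analysis set would still need stating.

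**What to change.** In section 7.2.1, prepare the allocation in advance but reveal it only when the infant has been deemed ready and the operator and first intended limb have been recorded. Infants lost before that moment are not randomised and are replaced.

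In section 8.3, state that every randomised infant is analysed in the assigned group, including those now withdrawn under sections 3.3.1 and 7.2.1, subject to any withdrawal of permission. State in advance how the primary outcome is coded for infants whose attempts were interrupted.

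The cost is protocol wording and some logistics. The device must be at hand for every consented infant, and someone other than the operator must open the allocation so that access is not delayed. Replacing even all 21 infants would take 21/600 = 3.5% of the lower figure in section 16.2 for potentially eligible children. Clinical management of complications is unchanged.
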